10.5. Search Criteria for TEAE of Special Interest/TEAE Syndrome¹

AESI	Search Criteria
Anaphylactic reactions	
For SMQ “anaphylactic reaction” An algorithmic approach will be used. A case must include either:
 
 1. A narrow term (a term from Category A); 2. Patient with both a term from Category B AND a term from Category C; 3. Patient with a term from Category D AND { a term from Category B - OR a term from Category C } 
For bullets 2 and 3, the search terms that are included under the SMQ for a particular event need to have the same start date (for e.g. if search shows cough (category B term) occurring at day 3 and urticaria (category C term) occurring at day 7, this event is not adjudicated as anaphylactic reaction as this is inconsistent with the clinical presentation of anaphylaxis as an acute event with simultaneous involvement of 2 or more body systems.
 
Note: manual adjudication of relevant PTs will be required by the study medical monitor, before database lock

Systemic or severe hypersensitivity reactions	
Hypersensitivity: Narrow SMQ for hypersensitivity excluding preferred term equal to dermatitis atopic or eczema
 
For systemic hypersensitivity, events in which 2 or more body systems are involved (as defined by System Organ Class) would be considered for adjudication based on further medical judgement
 
For severe hypersensitivity, an additional search will be done;
 
 - HLT = Injection site reactions and Severity = “severe” - HLT = Allergies to foods, food additives, drugs and other chemicals and Severity = “severe” or Serious=“Yes” 
Note: manual adjudication of relevant PTs will be required by the study medical monitor, before database lock

Malignancy	
 • SMQ “Malignant tumours” • SMQ “Tumours of unspecified malignancy”
Helminthic infections ²	-HLT = Cestode infections

	
-HLT = Helminthic infections NEC
 
-HLT = Nematode infections
 
-HLT = Trematode infection

Suicidal behavior	
Include the following PTs
 
 • Completed suicide • Suicidal ideation • Suicide attempt • Depression suicidal • Suicidal behavior
Any type of conjunctivitis or blepharitis (severe or serious)	
broad CMQ conjunctivitis (Conjunctivitis, Conjunctivitis allergic, Conjunctivitis bacterial, Conjunctivitis viral, Atopic keratoconjunctivitis, Blepharitis, Dry eye, Eye irritation, Eye pruritus, Lacrimation increased, Eye discharge, Foreign body sensation in eyes, Photophobia, Ocular hyperaemia, Conjunctival hyperaemia, Xerophthalmia)
 
Blepharitis PTs (Blepharitis, blepharitis allergic)
 
AND
 
Serious AE= “Yes” OR Severity= “severe”
 
Note: manual adjudication of relevant PTs will be required by the study medical monitor, before database lock.

Keratitis	
Any of the following PTs:
 
 a. Keratitis b. Allergic keratitis c. Ulcerative keratitis d. Atopic keratoconjunctivitis e. Herpes ophthalmic f. – Ophthalmic herpes simplex 
Note: manual adjudication of relevant PTs will be required by the study medical monitor, before database lock.

¹ The search criteria are meant to assist the process of identification of TEAE of Special Interest/TEAE Syndrome. However, since these criteria might not be exhaustive in some cases or may not be specific in other cases. Hence an additional blinded review of all PTs in the database may be performed by the Medical monitor, based on medical judgement, to identify any TEAE of Special Interest/TEAE Syndrome that might have been missed by the criteria or to identify any TEAE may been inaccurately assigned as AESI by the algorithmic search

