#### 3.2.4.2. Risks

Of the adverse drug reactions identified in the dupilumab adult AD clinical program, injection site reactions were very common ( $\geq 10\%$ ). Common adverse reactions ( $\geq 1\%$  and  $< 10\%$ ) included conjunctivitis, allergic conjunctivitis, eye pruritus, blepharitis, oral herpes, eosinophilia, and headache.

Serum sickness and serum sickness-like reactions occurred very rarely ( $< 0.01\%$ ) (Dupixent [SmPC], 2017).

In the pediatric trial, the safety profile was consistent with that reported in adults. There were no new safety signals detected with dupilumab in the pediatric population.

One serious case each of serum sickness and serum sickness-like reaction (both associated with high ADA titers) were reported in adult AD studies. Additionally, there has been 1 report of anaphylaxis considered related to study drug by the investigator in an asthma study (Dupilumab [Investigator Brochure, 2017]). No AEs of systemic hypersensitivity were reported in the pediatric study. In study R668-AD-1652, patients will be monitored at the trial site for 2 hours post-dose for the first 3 visits at which study drug is administered to facilitate detection and treatment of any immediate hypersensitivity reactions to the study drug.

A higher incidence of conjunctivitis-related events has been observed in dupilumab-treated subjects as compared to placebo in the AD studies. A predominant number of these cases were non-serious, mild to moderate in severity, reported recovered/recovering during the active study periods, and infrequently led to study drug discontinuation. Neither a consistent dose response nor a consistent time to onset of these events have been observed.

Similarly, a higher incidence of injection site reactions has been observed in the dupilumab treated subjects, consistent with the subcutaneous injection of a protein biologic. There have been no serious events of ISR, and these events have infrequently led to study drug discontinuation (Dupilumab [Investigator Brochure, 2017]).

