- Treatment-emergent AEs (TEAEs) are AEs that developed or worsened in severity compared to the baseline during the treatment and follow-up period. As only the worsening pre-existing AEs and new AEs reported during the treatment and follow-up period will be collected in the study, all AEs collected during the treatment and follow-up period are considered as TEAEs.
- TEAEs during the 16 week treatment period are AEs with onset after the first dose up to the week 16 visit date (study day 113 if the week 16 visit date is missing) or early termination visit whichever is earlier. TEAEs that have an onset during the 16 week treatment period and continued afterwards into follow-up period will be counted only once as TEAEs during the 16 week treatment period.
- TEAEs during the Follow-up period are AEs with onset after the week 16 visit date up to the end of study.

Adverse event of special interest (AESI)/TEAE category

- Systemic or extensive hypersensitivity reactions, including anaphylactic reactions
- Malignancy
- Helminthic infections
- Suicide-related events
- Conjunctivitis (any type or etiology), keratitis or blepharitis (only events that are either severe or serious will be reported as AESIs)

[Appendix 10.5](#) provides a list of AESIs search criteria.

Other adverse events:

- Narrow conjunctivitis is defined as the following PT terms
 - Conjunctivitis
 - Conjunctivitis allergic
 - Conjunctivitis bacterial
 - Conjunctivitis viral
 - Atopic Keratoconjunctivitis
- Broad conjunctivitis is defined as the following PT terms
 - Conjunctivitis, Conjunctivitis allergic
 - Conjunctivitis bacterial
 - Conjunctivitis viral
 - Atopic Keratoconjunctivitis
 - Blepharitis
 - Dry eye
 - Eye irritation
 - Eye pruritus
 - Lacrimation increased
 - Eye discharge
 - Foreign body sensation in eyes
 - Photophobia, Xerophthalmia
 - Ocular hyperaemia
 - Conjunctival hyperaemia
- Keratitis is defined as the following PT terms
 - Keratitis
 - Allergic keratitis
 - Ulcerative keratitis
 - Corneal infection
 - Atopic keratoconjunctivitis
 - Herpes ophthalmic
- Eczema Herpeticum is defined as the following PT terms
 - Eczema herpeticum

- Herpes Zoster is defined as the following PT terms
 - Herpes zoster
 - Ophthalmic herpes zoster
- Muco-cutaneous herpes simplex infections is defined as the following PT terms
 - Oral herpes
 - Genital herpes
 - Herpes simplex
 - Herpes virus infection
 - Nasal herpes

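### The SAP 10.5 hypersensitivity search uses severity where the AESI definition uses extent, so the AESI table may not match the trial's own definition

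*SAP*

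**What the plan says.** Protocol 9.4.3 and the AESI list in SAP 4.5.1 use the same words for this event: "Systemic or extensive hypersensitivity reactions, including anaphylactic reactions". SAP 4.5.1 then sends the reader to Appendix 10.5, which it says "provides a list of AESIs search criteria".

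Appendix 10.5 gives anaphylaxis its own row. The rest of the definition is covered by a row labelled "Systemic or severe hypersensitivity reactions". That row contains:

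- a starting set: "Narrow SMQ for hypersensitivity excluding preferred term equal to dermatitis atopic or eczema";
- a systemic branch: "For systemic hypersensitivity, events in which 2 or more body systems are involved (as defined by System Organ Class) would be considered for adjudication";
- a severe branch, described as an additional search, with two lines. One begins "HLT = Injection site reactions and Severity" and requires the grade severe. The other takes events under the high-level term for food, drug and chemical allergies if they are severe or serious;
- a closing note that makes manual adjudication of relevant preferred terms by the study medical monitor mandatory before database lock.

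Footnote 1 to the appendix says that the criteria are an aid and may be neither exhaustive nor specific. It permits, but does not require, a further blinded review of all preferred terms to add missed events or correct wrongly assigned ones.

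**The concern.** A search should implement the definition it serves. Here the definition turns on how widespread the reaction is, and the search turns on how severe it is. These are different properties: a reaction can cover much of the skin and be graded moderate, or be confined to one injection site and be graded severe.

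What is at stake is a safety output. SAP 5.8.1 plans AESI incidence by category and Kaplan-Meier estimates of time to first AESI. It also plans Cox hazard ratios for selected adverse events, in order to detect safety signals. If the search and the definition pick out different events, these outputs describe a category that the protocol did not define. They may also disagree with the 24-hour AESI reports, which investigators make under the protocol wording. SAP 1.2.3 declares no modifications from the protocol's statistical section, so nothing announces the difference as a deliberate change.

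**Working it through.** No arithmetic applies. The check sets the definition beside the search and follows two event types through the row.

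**Definition against search**

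| Element | Protocol 9.4.3 and SAP 4.5.1 | SAP 10.5 |
|---|---|---|
| Systemic | Yes | Yes: two or more system organ classes |
| Extensive | Yes | No criterion anywhere in the appendix |
| Severe | Not mentioned for hypersensitivity | Yes: in the label and in its own branch |
| Anaphylaxis | Yes | Yes: separate row, not affected |

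The eye-disorder AESI is a useful contrast. Its definition does restrict the event to severe or serious cases, and the conjunctivitis and blepharitis search applies the same restriction. The hypersensitivity definition has no such restriction, so the severity standard in its row has no source in the definition.

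**Two events traced through the row**

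Event A is a widespread skin reaction in one organ class, graded moderate and not serious. It is assumed that its preferred term is in the narrow SMQ (the documents do not list the SMQ's terms) and that it is not coded under the two high-level terms of the severe branch. Event B is a purely local injection-site reaction graded severe.

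| Step in SAP 10.5 | Event A | Event B |
|---|---|---|
| Narrow SMQ, no severity or extent filter | Retrieved | Not needed for the result |
| Two or more organ classes | Fails | Fails |
| Severe branch | Fails | Retrieved, with no systemic or extent condition |
| Mandatory adjudication of relevant terms | Only if the monitor treats the term as relevant | Candidate; no stated ground to accept or reject |
| Optional blinded review of all terms | May be recovered, if the review is done | May be removed, if the review is done |

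For event A, the definition can be met and yet no written criterion carries the event to adjudication. It is not barred, but its route depends on discretion.

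For event B, the injection-site grading scale in protocol 9.5.1 shows how it arises: erythema or induration of more than 10 cm is enough for the grade severe. The event then becomes a candidate by severity alone. The adjudicator has a row label that says severe and a definition that says extensive, and neither document says what extensive means.

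**The case against.** The strongest reply is that SAP 10.5 is only a search aid. SAP 4.5.1 keeps the protocol definition unchanged, footnote 1 admits that the criteria are imperfect, and adjudication is mandatory. On this view the mismatch is a label. Part of this stands, and it rules out several stronger readings that a reader might infer:

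- *That the SAP has replaced the protocol definition.* It has not. Section 4.5.1 still carries it, so the conflict is inside the SAP as well as with the protocol.
- *That extensive, non-severe reactions are excluded from adjudication.* The narrow-SMQ step has no severity filter, and both the mandatory note and the optional review leave room to reach them. One could even read the row as sending every narrow-SMQ hit to the monitor. The text does not say so, and the sentence that directs multi-organ-class events to adjudication would then have little purpose.
- *That severe local injection-site reactions are counted as AESIs.* They are candidates for adjudication only. They are also not all trivial or local: the protocol's severe grade includes necrosis, exfoliative dermatitis and events that need hospitalization. Screening them is defensible, and removing them automatically from the AESI count would be hard to justify.
- *That the between-arm comparison is biased, and against dupilumab.* Protocol 3.2.4.2 does say that "a higher incidence of injection site reactions has been observed in the dupilumab treated subjects", but that concerns injection-site reactions of any grade. The same section reports no serious ones. The documents give no rate of severe reactions in children and no indication of how adjudication would fall.

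Other outputs also limit the damage. All treatment-emergent events are tabulated by organ class, term and severity (SAP 5.8.1). Narrow-SMQ hypersensitivity is summarized by anti-drug antibody status without a severity filter (SAP 5.11.2). The events stay visible; it is their AESI label that is uncertain.

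What does not stand is the claim that this is only a label. The branches follow the label, and the safeguards give the monitor no criterion for extent.

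**Conclusion.** The point holds as a conflict between a stated search rule and the definition it implements. Two consequences follow from the text. First, no prespecified criterion sends an extensive, single-organ-class, non-severe, non-serious reaction to adjudication. Second, severe injection-site reactions become candidates under a standard that is absent from the definition, with no stated basis for deciding on a purely local one. The AESI table can therefore differ from the trial's own definition.

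The size and direction of any effect on the between-arm comparison cannot be stated. A reader might try to size it from the planned 110 patients per group, where each 1% would be 110 × 0.01 = 1.1 children. But the documents give neither an event rate nor an acceptance rate at adjudication to apply, so no such figure is offered here.

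The conclusion assumes only that the branches in the row are meant to select what is adjudicated. The efficacy analyses and the hierarchical testing order are not affected.

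**What to change.** 1. Retitle the SAP 10.5 row so that it reads systemic or extensive, as in SAP 4.5.1 and protocol 9.4.3.
2. Send every narrow-SMQ hypersensitivity event, after the existing exclusions for atopic dermatitis and eczema, to the medical-monitor adjudication already planned. Do this blinded, and judge each event against that definition.
3. Fix a working meaning of extensive, in writing, before database lock. Without it, the instruction to judge against the definition cannot be applied consistently.
4. Keep the severe injection-site hits and the severe or serious food and drug allergy hits as candidates only. Count them as AESIs only if they are adjudicated as systemic or extensive, and otherwise report them separately.
5. In the same edit, correct the cross-reference in SAP 5.8.1. It points to Appendix 10.4 for the AESI categories, but that appendix holds the laboratory, vital-sign and ECG thresholds.

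The cost is a table edit and some additional blinded term review by the medical monitor. SAP section 1 allows revisions based on blinded review, with the plan finalized before the final database lock.

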### 9.4.3. Other Events that Require Accelerated Reporting

The following events also require reporting to the sponsor (or designee) within 24 hours of learning of the event:

**Symptomatic Overdose of Study Drug:** Accidental or intentional overdose of at least 2 times the intended dose of study drug within the intended therapeutic window, if associated with an AE.

**Pregnancy:** Although pregnancy is not considered an AE, it is the responsibility of the investigator to report to the sponsor (or designee), by telephone within 24 hours of identification, any pregnancy occurring in a female patient during the study or within 12 weeks of the last dose of study drug. Any complication of pregnancy affecting a female study patient and/or fetus and/or newborn that meets the SAE criteria must be reported as an SAE. Outcome for all pregnancies should be reported to the sponsor.

**Adverse Events of Special Interest:** Adverse events of special interest (AESI) must be reported within 24 hours of identification. Adverse events of special interest for this study include:

- Systemic or extensive hypersensitivity reactions, including anaphylactic reactions
- Malignancy
- Helminthic infections
- Suicide-related events
- Conjunctivitis (any type or etiology), keratitis, or blepharitis (only events that are either severe or serious will be reported as AESIs)

Any patient who experiences an adverse event of special interest related to an eye disorder will be referred to an ophthalmologist. Further evaluation of these AESIs will be performed including any additional tests, as per the discretion of the ophthalmologist.

Refer to the study reference manual for the procedures to be followed.

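### The SAP Appendix 10.5 keratitis search lacks the severe-or-serious condition that the protocol and SAP place on this AESI, so milder events can enter unless adjudication removes them

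*SAP*

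**What the plan says.** **Definition.** Protocol 9.4.3 lists the eye AESI as "Conjunctivitis (any type or etiology), keratitis, or blepharitis (only events that are either severe or serious will be reported as AESIs". SAP 4.5.1 repeats it almost word for word: "Conjunctivitis (any type or etiology), keratitis or blepharitis (only events that are either severe or serious will be reported as AESIs". The restriction covers all three conditions, keratitis included.

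**Link to the search.** After the AESI list, SAP 4.5.1 says that Appendix 10.5 "provides a list of AESIs search criteria".

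**Search.** Appendix 10.5 splits the eye AESI into two rows.
- The first is labelled "Any type of conjunctivitis or blepharitis (severe or serious" and adds to its term lists the condition "Serious AE= “Yes” OR Severity= “severe".
- The second is labelled Keratitis. It begins "Any of the following PTs" and lists six PTs. It states no severity or seriousness condition.

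Both rows carry the same note requiring manual adjudication of relevant PTs by the study medical monitor before database lock. Footnote 1 to the table describes the criteria as an aid to identification. It allows an additional blinded review that may find missed AESIs or events wrongly assigned as AESIs.

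**A second keratitis list.** Under the separate heading for other adverse events, SAP 4.5.1 says "Keratitis is defined as the following PT terms" and gives six PTs of its own.

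**Use.** SAP 5.8.1 plans an AESI summary by category and by SOC/PT, and Kaplan-Meier estimates of time to first AESI. It also plans Cox hazard ratios for selected adverse events.

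**The concern.** A search that puts a definition into operation should select what the definition selects. Here one row does and the next does not, although one restriction governs both. A programmer who follows the appendix and an adjudicator who follows 4.5.1 would reach different AESI sets, and the plan does not say which prevails.

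Eye events will be read closely in this trial. Protocol 3.2.4.2 reports more conjunctivitis-related events on dupilumab than on placebo in earlier atopic dermatitis studies, mostly mild to moderate. Under Protocol 9.4.3, sites report eye AESIs within 24 hours, and refer those patients to an ophthalmologist, on the severe-or-serious definition. An unfiltered search could put into the analysis AESI set events that no site was asked to report as AESIs.

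Nothing suggests that keratitis was deliberately treated differently. The amendment history explains the current eye definition by saying that mild to moderate events in earlier trials were not clinically meaningful, even when prolonged. That reasoning argues for the filter in both rows.

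**Working it through.** The plan states no figure on this point, so there is none to reproduce. The check compares the rules case by case and then compares the two term lists.

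**1. Severity by seriousness.** Three severities (Protocol 9.5.1) times serious yes/no gives 3 × 2 = 6 patterns. For an event coded to a PT listed in the row concerned:

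| Pattern | AESI by definition (Protocol 9.4.3, SAP 4.5.1) | Selected by conjunctivitis/blepharitis row | Selected by keratitis row |
|---|---|---|---|
| Mild, non-serious | No | No | Yes |
| Mild, serious | Yes | Yes | Yes |
| Moderate, non-serious | No | No | Yes |
| Moderate, serious | Yes | Yes | Yes |
| Severe, non-serious | Yes | Yes | Yes |
| Severe, serious | Yes | Yes | Yes |
| **Total** | **4 of 6** | **4 of 6** | **6 of 6** |

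The excess is 6 − 4 = 2 patterns: mild non-serious and moderate non-serious. With the neighbouring row's condition added, the keratitis row selects the same four patterns as the definition.

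**2. The overlapping term.** *Atopic keratoconjunctivitis* is the only PT in both Appendix 10.5 eye rows. A mild non-serious event with this code fails the conjunctivitis/blepharitis row and passes the keratitis row. This follows from the missing condition and is not a further error: SAP 4.5.1 itself puts the term in its narrow conjunctivitis, broad conjunctivitis and keratitis lists.

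**3. The two keratitis lists.**
- In both (5): *Keratitis*, *Allergic keratitis*, *Ulcerative keratitis*, *Atopic keratoconjunctivitis*, *Herpes ophthalmic*.
- Only in SAP 4.5.1 (1): *Corneal infection*.
- Only in Appendix 10.5 (1): *Ophthalmic herpes simplex*.

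Each list has 5 + 1 = 6 terms. A severe *Corneal infection* would therefore count as keratitis in the 4.5.1 grouping but would not be picked up by the 10.5 keratitis row. This is separate from the severity question, because neither extra term brings in milder events.

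**4. Path to the analyses.** SAP 4.5.1 sends the reader to Appendix 10.5 for the AESI search. The AESI summary line in SAP 5.8.1 cites Appendix 10.4, which holds the laboratory, vital-sign and ECG thresholds. I take 10.5 to be meant.

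**The case against.** The strongest reply is that Appendix 10.5 is a screen and not the final count. The keratitis row requires manual adjudication before database lock. Footnote 1 concedes that the criteria may not be specific and provides for review of wrongly assigned events. The definition in Protocol 9.4.3 and SAP 4.5.1 still stands, so the adjudicator has a written rule available. A reader might infer from the bare term list that mild keratitis will be counted, or that every mild or moderate event is an excess AESI. The documents do not support that, because the search does not fix the outcome.

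The reply does not remove the gap. The adjudication note covers relevant PTs and gives no severity rule. The conjunctivitis/blepharitis row has the same note and still carries an explicit condition. The footnote review is optional and rests on medical judgement.

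Three further objections stand as limits on the point:
- The 4.5.1 keratitis list is a separate grouping under other adverse events. A reader might take it for the AESI definition, or think that the list difference lets milder events in. Neither follows: the AESI definition names no PTs.
- Keratitis has its own row, AESIs are tabulated by category, and SAP 5.8.1 also plans TEAEs by severity, severe TEAEs and serious TEAEs. Any unfiltered events would therefore be visible, and the severe or serious ones could be recovered.
- The hazard ratios are for selected events, and nothing says that keratitis is among them.

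**Conclusion.** The point holds in a limited form. The Appendix 10.5 keratitis search omits a condition that the protocol, the SAP text and the neighbouring row all apply. Non-serious mild and moderate keratitis events, including *Atopic keratoconjunctivitis* events that fail the filtered row, can enter the AESI summary and the time-to-first-AESI analysis unless adjudication removes them. The one-term differences between the lists are a separate and smaller inconsistency.

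The number of patients affected cannot be estimated. The documents give no keratitis counts and do not say what severity rule the adjudicator will use. With about 110 patients per group, one patient is 1/110 = 0.9 percentage points, but that is the weight of any single patient and not a forecast of the excess. Any error from the missing condition is towards over-counting a safety event. Efficacy results, power and Type 1 error control are unaffected.

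The conclusion assumes that the Protocol 9.4.3 definition governs the analysis AESI set, as SAP 4.5.1 indicates by repeating it, and that 10.5 is the appendix meant in SAP 5.8.1.

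**What to change.** 1. In the Appendix 10.5 keratitis row, add after the term list: AND (Serious AE = Yes OR Severity = severe). Alternatively, state that rule in the row's adjudication note.
2. Keep keratitis of all severities in the SAP 4.5.1 grouping for other adverse events. No safety information is then lost from the report.
3. Separately, reconcile the keratitis lists in 4.5.1 and 10.5, or explain why *Corneal infection* is only in the former and *Ophthalmic herpes simplex* only in the latter. A reader might assume that the union of the lists is intended. The documents do not settle that, and it would widen the AESI search, so the choice should be stated on medical grounds.

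The cost is one line in an appendix and one list check, made before database lock. No data collection changes.
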